11.2 Study Files and Subject Source Documents

Subject confidentiality is strictly held in trust by the participating investigators, research staff, Vergent and their designees. This confidentiality is extended to cover testing of biological samples in addition to the clinical information relating to subjects. Authorized representatives of Vergent may inspect all documents and records required to be maintained by the Investigator, including but not limited to, medical records (office, clinic, or hospital) and pharmacy records for the subjects in this study. Any data, specimens, forms, reports, and other records that leave the site will be identified only by a subject identification number to maintain confidentiality.

The Investigator must maintain adequate and accurate records to enable the conduct of the study to be fully documented and the study data to be subsequently verified. These documents include Investigators' Study Files and original subject clinical source documents generated at the study site. The term "original" means the first recording of the data.

The Investigator will ensure the site master files are maintained, including the study protocol and its amendments, IRB/HREC and regulatory approvals with associated correspondence, informed consents, study drug records, staff curriculum vitae, all correspondence, and other appropriate documents.

Subject clinical source documents may include, but are not limited to, subject hospital/clinic records, physicians' and nurses' notes, appointment books, laboratory reports, ECGs, radiographs, and consultant letters. The Investigator must assure that all original source documents are available to support monitoring activities.

11.3 Monitoring

During the study monitoring will occur on a regular basis as agreed to by the site. Monitoring visits may be conducted on site or remotely, via a secured internet connection. For this study, at least 2 monitoring visits must be conducted on site, unless otherwise agreed to by Vergent, in writing. Monitoring visits will be conducted according to the applicable ICH and GCP guidelines to ensure protocol adherence, quality of data, drug accountability, compliance with regulatory requirements and continued adequacy of the investigational site and its facilities. The Investigator will cooperate in the monitoring process by ensuring the availability of the eCRFs, source documents and other necessary documents at the time of the monitoring visits and by prompt attention to any matters brought to his/her attention by the monitor.

11.4 Audit

ICH guidelines for GCP require independent inspection of clinical program activities. Such inspections may be performed at any time - before, during and/or after the study. The Investigator and study staff are responsible for maintaining the site master file containing all study-related regulatory documentation as outlined by Vergent that will be suitable for

inspection at any time by Vergent, its designees, and/or regulatory agencies. The Investigator understands and agrees to give access to the necessary documentation and files.

11.5 Retention of Data

Institution shall maintain all Study Data for a period of ten (10) years following the Completion Date. Without limiting the foregoing, Institution and Principal Investigator will at a minimum retain Study Data to the extent and for the periods required under Applicable Law, including 21 C.F.R. § 312.62(c). Institution will take reasonable and customary precautions, including the application of cybersecurity measures, password protection, and periodic back-up of computer files and storage of all records and files in a secure area reasonably protected from fire, theft, destruction, and unauthorized access to prevent the loss or alteration of any Study Data..

12. PUBLICATION POLICY AND SHARING OF DATA

Table 1: Summary of Data Collection and Analysis							
Study ID	Participant Demographics		Intervention Details			Outcome Measures	Statistical Analysis
	Age (Mean)	Gender (Male/Female)	Duration (Weeks)	Frequency (Times/Week)	Intensity (Level)		
001	25.5	15M/15F	12	3	High	Pre-Test, Post-Test	T-Test
002	28.2	20M/20F	8	2	Medium	Pre-Test, Post-Test, Follow-Up	ANOVA
003	30.1	25M/25F	10	4	High	Pre-Test, Post-Test	T-Test
004	32.5	30M/30F	6	1	Low	Pre-Test, Post-Test	T-Test
005	35.0	35M/35F	12	3	Medium	Pre-Test, Post-Test, Follow-Up	ANOVA
006	37.5	40M/40F	9	2	High	Pre-Test, Post-Test	T-Test
007	40.0	45M/45F	11	3	Medium	Pre-Test, Post-Test	T-Test
008	42.5	48M/48F	7	1	Low	Pre-Test, Post-Test	T-Test
009	45.0	50M/50F	10	2	High	Pre-Test, Post-Test, Follow-Up	ANOVA
010	47.5	55M/55F	12	3	Medium	Pre-Test, Post-Test	T-Test
011	50.0	60M/60F	8	1	Low	Pre-Test, Post-Test	T-Test
012	52.5	65M/65F	10	2	High	Pre-Test, Post-Test	T-Test
013	55.0	70M/70F	12	3	Medium	Pre-Test, Post-Test, Follow-Up	ANOVA
014	57.5	75M/75F	9	1	Low	Pre-Test, Post-Test	T-Test
015	60.0	80M/80F	11	2	High	Pre-Test, Post-Test	T-Test
016	62.5	85M/85F	7	1	Low	Pre-Test, Post-Test	T-Test
017	65.0	90M/90F	10	2	High	Pre-Test, Post-Test, Follow-Up	ANOVA
018	67.5	95M/95F	12	3	Medium	Pre-Test, Post-Test	T-Test
019	70.0	100M/100F	8	1	Low	Pre-Test, Post-Test	T-Test
020	72.5	105M/105F	10	2	High	Pre-Test, Post-Test	T-Test
021	75.0	110M/110F	12	3	Medium	Pre-Test, Post-Test, Follow-Up	ANOVA
022	77.5	115M/115F	9	1	Low	Pre-Test, Post-Test	T-Test
023	80.0	120M/120F	11	2	High	Pre-Test, Post-Test	T-Test
024	82.5	125M/125F	7	1	Low	Pre-Test, Post-Test	T-Test
025	85.0	130M/130F	10	2	High	Pre-Test, Post-Test, Follow-Up	ANOVA
026	87.5	135M/135F	12	3	Medium	Pre-Test, Post-Test	T-Test
027	90.0	140M/140F	8	1	Low	Pre-Test, Post-Test	T-Test
028	92.5	145M/145F	10	2	High	Pre-Test, Post-Test	T-Test
029	95.0	150M/150F	12	3	Medium	Pre-Test, Post-Test, Follow-Up	ANOVA
030	97.5	155M/155F	9	1	Low	Pre-Test, Post-Test	T-Test
031	100.0	160M/160F	11	2	High	Pre-Test, Post-Test	T-Test
032	102.5	165M/165F	7	1	Low	Pre-Test, Post-Test	T-Test
033	105.0	170M/170F	10	2	High	Pre-Test, Post-Test, Follow-Up	ANOVA
034	107.5	175M/175F	12	3	Medium	Pre-Test, Post-Test	T-Test
035	110.0	180M/180F	8	1	Low	Pre-Test, Post-Test	T-Test
036	112.5	185M/185F	10	2	High	Pre-Test, Post-Test	T-Test
037	115.0	190M/190F	12	3	Medium	Pre-Test, Post-Test, Follow-Up	ANOVA
038	117.5	195M/195F	9	1	Low	Pre-Test, Post-Test	T-Test
039	120.0	200M/200F	11	2	High	Pre-Test, Post-Test	T-Test
040	122.5	205M/205F	7	1	Low	Pre-Test, Post-Test	T-Test
041	125.0	210M/210F	10	2	High	Pre-Test, Post-Test, Follow-Up	ANOVA
042	127.5	215M/215F	12	3	Medium	Pre-Test, Post-Test	T-Test
043	130.0	220M/220F	8	1	Low	Pre-Test, Post-Test	T-Test
044	132.5	225M/225F	10	2	High	Pre-Test, Post-Test	T-Test
045	135.0	230M/230F	12	3	Medium	Pre-Test, Post-Test, Follow-Up	ANOVA
046	137.5	235M/235F	9	1	Low	Pre-Test, Post-Test	T-Test
047	140.0	240M/240F	11	2	High	Pre-Test, Post-Test	T-Test
048	142.5	245M/245F	7	1	Low	Pre-Test, Post-Test	T-Test
049	145.0	250M/250F	10	2	High	Pre-Test, Post-Test, Follow-Up	ANOVA
050	147.5	255M/255F	12	3	Medium	Pre-Test, Post-Test	T-Test

[illegible]

ATTACHMENT B: SUMMARY OF CHANGES

Protocol Version	Location in Protocol	Original Text	Modified Text	Reason for Change
V1.0, 15JUNE2023 to V2.0, 14August2023,	[REDACTED]	[REDACTED]	[REDACTED]	[REDACTED]
	[REDACTED]	[REDACTED]	[REDACTED]	[REDACTED]
	[REDACTED]	[REDACTED]	[REDACTED]	[REDACTED]
	[REDACTED]	[REDACTED]	[REDACTED]	[REDACTED]
	[REDACTED]	[REDACTED]	[REDACTED]	[REDACTED]

	[REDACTED]	[REDACTED]	[REDACTED]	[REDACTED]
	[REDACTED]	[REDACTED]	[REDACTED]	[REDACTED]
	[REDACTED]	[REDACTED]	[REDACTED]	[REDACTED]
V2.0, 14AUGUST2023 to V3.0, 15MARCH2024	[REDACTED]	[REDACTED]	[REDACTED]	[REDACTED]
	[REDACTED]	[REDACTED]	[REDACTED]	[REDACTED]

		[REDACTED]	[REDACTED]	[REDACTED]
		[REDACTED]	[REDACTED]	
	[REDACTED]	[REDACTED]	[REDACTED]	[REDACTED]
	[REDACTED]	[REDACTED]	[REDACTED]	[REDACTED]
	[REDACTED]	[REDACTED]	[REDACTED]	[REDACTED]
	[REDACTED]	[REDACTED]	[REDACTED]	[REDACTED]

	[REDACTED]	[REDACTED]	[REDACTED]	[REDACTED]
	[REDACTED]	[REDACTED]	[REDACTED]	[REDACTED]

	
[REDACTED]
	
[REDACTED]
	
[REDACTED]
	
[REDACTED]

	
[REDACTED]
	
[REDACTED]
	
[REDACTED]
	
[REDACTED]

	
[REDACTED]
	
[REDACTED]
	
[REDACTED]
	
[REDACTED]

## LIST OF ABBREVIATIONS

AE	Adverse Event
AR	Adverse Reaction
AUC	Area under the curve
BMI	Body mass index
BPM	Beats per minute
CDER	Center for Drug Evaluation and Research
CHMP	Committee for Medicinal Products for Human Use
CPMP	Committee for Proprietary Medicinal Products
CRF	Case report form
CRO	Contract research organization
CSE	Clinically Significant Event
CSR	Clinical study report
CT	Computed Tomography
CTCAE	Common Terminology Criteria for Adverse Events
DMC	Data monitoring committee
ECG	Electrocardiogram
FN	False Negative
FP	False Positive
FR	Federal Register
GEE	Generalized Estimating Equation
HLT	High level term
ICH	International Conference on Harmonisation of Technical Requirements for Registration of Pharmaceuticals for Human Use
ITT	Intent to treat
IVRS/IWRS	Interactive voice/web response system
LLT	Lower level term
MedDRA	Medical dictionary for regulatory activities
NIR	Near-Infrared
NPV	Negative Predictive Value
PPV	Positive Predictive Value
PT	Preferred term
ROC	Receiver Operating Characteristic
SAP	Statistical analysis plan
SOC	System organ class
TFLs	Tables, figures, and listings
TN	True Negative
TP	True Positive
WHO	World Health Organization

## 1. INTRODUCTION

This statistical analysis plan (SAP) describes the statistical analysis methods and data presentations to be used in tables, figures, and listings (TFLs) to be implemented during the analyses of data collected within the scope of Protocol VGT-309-2B-2023 [A Phase 2, Multi-center, Open-label Study to Evaluate the Safety and Efficacy of VGT-309, a Tumor-Targeted, Activatable Fluorescent Imaging Agent, in Subjects Undergoing Surgery for Cancer in the Lung] sponsored by Vergent Bioscience, Inc. This SAP will be finalized before database lock. Any deviations from this plan after SAP finalization will be documented in the clinical study report (CSR).

## 2. STUDY OBJECTIVES

### 2.1. Primary Efficacy Objective

Assess the efficacy of VGT-309 with near-infrared (NIR) imaging for lesion visualization when compared to standard surgical techniques in subjects undergoing surgery for proven or suspected cancer in the lung.

### 2.2. Secondary Efficacy Objective

Assess the utility of VGT-309 with NIR imaging to identify cancerous tissue as confirmed by histopathology.

### 2.3. Safety Objective

Determine the safety and tolerability of VGT-309 in subjects with proven or suspected cancer in the lung.

## 3. STUDY ENDPOINTS

### 3.1. Primary Efficacy Endpoint

Identify the proportion of subjects with at least one Clinically Significant Event (CSE) as defined by:

1. Intraoperative localization of one or more preoperatively identified lung lesions using VGT-309 with NIR imaging when standard surgical techniques using white light and/or palpation failed to identify the lesion(s), and lesion(s) are confirmed by histologic examination to be other than normal lung tissue.
2. Identification of one or more synchronous or occult lung lesions using VGT-309 with NIR imaging when standard surgical techniques using white light and/or palpation and preoperative imaging failed to identify the lesion(s), and lesion(s) are confirmed by histologic examination to be cancerous or precancerous.
3. Identification of fluorescence within  $\leq 10$  mm from the inside edge of the closest staple line as measured by the investigator *ex vivo* in the operating room using NIR imaging, with pathologic margin confirmed by histologic examination to be  $\leq 10$  mm.

NOTE: Margins from excisions of known or suspected metastases at the time of the surgery, OR diagnostic wedge resections where a completion lobectomy or segmentectomy was subsequently performed, will not be considered for Margin CSE inclusion.

4. Identification of lymph nodes by VGT-309 with NIR imaging confirmed by histologic examination to be cancerous.

### 3.2. Secondary Efficacy Endpoints

To evaluate the sensitivity, positive predictive value (PPV), and 1-PPV of VGT-309 with NIR imaging for lesion(s) *in vivo*:

1. Sensitivity is defined as the probability that the tissue fluoresces when it is cancer, as confirmed by histology  $(TP/(TP+FN))$  \*
2. Positive predictive value (PPV) is defined as the probability that a tissue sample contains cancer on histologic exam if it fluoresces  $((TP/(TP+FP))$  \*
3. 1-Positive predictive value (1-PPV) is defined as the probability that a tissue sample does not contain cancer when it fluoresces  $((FP/(TP+FP))$  \*

\* TP = true positive, FP = false positive, FN = false negative

[REDACTED]

[REDACTED]

[REDACTED]

[REDACTED]

[REDACTED]

[REDACTED]

[REDACTED]

[REDACTED]

[REDACTED]

[REDACTED]

### 3.4. Safety Endpoint

Assessment of clinical laboratory tests, physical exam results, ECGs and vital sign measurements at various time points during the study, and documentation of treatmentemergent adverse events.

## 4. STUDY DESIGN

This is a Phase 2, multi-center, open-label study to evaluate the safety and efficacy of VGT-309, a tumor-targeted, activatable fluorescent imaging agent, in subjects undergoing surgery for proven or suspected cancer in the lung. Approximately 100 subjects will be enrolled to ensure at least 86 subjects are evaluable with the option to expand enrollment by protocol amendment if deemed necessary by the DSC (Data Safety Committee) to meet primary and/or secondary objectives.

Following agreement with and signing of the informed consent, subjects will undergo screening measurements for the study within 4 weeks prior to the anticipated dosing:

1. Medical, surgical and medication history.
2. Complete physical exam, including vital signs and height
3. Weight (needed for dose calculation)
4. Chemistry, hematology, coagulation and urinalysis with microscopy clinical laboratory studies.
5. 12-lead ECG.
6. Serum pregnancy test for females of child-bearing potential.

After meeting all enrollment criteria, each subject will receive 0.32 mg/kg VGT-309 by IV administration 12-36 hours prior to the induction of general anesthesia for surgery (refer to section 4 of protocol v3.0). Subjects will be observed for 1 hour after dosing is completed and asked about possible treatment emergent adverse events.

Subjects will undergo surgical resection within 12-36 hours after completion of VGT-309 dosing. Measurements of efficacy will be taken during surgery and during the pathological examination of all surgical specimens.

Following surgery, subjects will be monitored for safety during their hospitalization. Between 7 to 14 and 25 to 35 days after surgery, the subjects will return to the clinic or have a telehealth visit for final safety assessments. At the last visit, if there are no adverse events requiring further follow up, subjects will then be released from the study.

If a subject chooses to withdraw from the study prior to the final visit, they will be asked to undergo a final safety assessment before their departure.

## **5. DETERMINATION OF SAMPLE SIZE**

[REDACTED]

## **6. TYPE OF PLANNED ANALYSIS**

This analysis plan outlines planned analysis procedures for the Final Analysis, as described below. Data outliers and other raw data issues are planned to be identified and logged on a rolling basis throughout the study, with appropriate resolution decided upon and documented prior to the planned analyses outlined below. The Final Analysis will take place after the study is completed and the database has been locked. All tables, figures, and listings described in this SAP are planned to be included in the final analysis.

## 7. GENERAL CONSIDERATIONS FOR DATA ANALYSES

### 7.1. Data Presentation and Summarization

The statistical analyses will be reported using summary tables, listings, and figures (TLFs). The International Conference on Harmonisation (ICH) numbering convention will be used for all TLFs. Continuous variables will be summarized with means, standard deviations, medians, minimums, and maximums. Other summaries (e.g., quartiles, 5%, 95% intervals, CV or %CV) may be used as appropriate. Categorical variables will be summarized by counts and by percentage of patients in corresponding categories. Summaries will generally be presented by treatment cohort and for all participants overall. P-values will be presented for hypothesis testing, with a value of 0.05 being the threshold of significance under which the null hypothesis can be rejected. Descriptive statistics will be rounded to two decimal places with the exception of standard deviation which will be rounded to three decimal places.

All analyses and tabulations will be performed using SAS® Version 9.4 or higher. Tables, listings, and figures will be provided in PDF format.

### 7.2. Missing or incomplete dates

The most conservative approach will be systematically considered. [REDACTED]

[REDACTED]  
[REDACTED]  
[REDACTED]  
[REDACTED]

[REDACTED]  
[REDACTED]

[REDACTED]

- [REDACTED]  
[REDACTED]  
[REDACTED]  
[REDACTED]  
[REDACTED]

- [REDACTED]  
[REDACTED]  
[REDACTED]  
[REDACTED]  
[REDACTED]

- [REDACTED]  
[REDACTED]

[REDACTED]

- [REDACTED]
- [REDACTED]
- [REDACTED]

### 7.3. Analysis Populations

Analysis populations define the participants to be included in an analysis. Analysis populations and their definitions are provided in this section. The analysis population will be identified and included as a subtitle of each table.

Inclusion in the analysis population will be determined prior to database lock. A summary of the number and percent of participants in each analysis population will be provided. A by-participant listing of each analysis population will also be provided.

#### 7.3.1. Enrolled Population

This population consists of all subjects who are enrolled in the study (signed informed consent).

#### 7.3.2. Safety Population

This population consists of all subjects who received any amount of VGT-309.

#### 7.3.3. Intent to Treat (ITT) Population

This population will consist of all subjects who received any amount of VGT-309 and had surgery with NIR imaging after the surgeon first attempts to locate the tumor/nodule by white light and palpation.

#### 7.3.4. Evaluable Population

The Evaluable Population (EP) will consist of the subset of ITT subjects who were eligible, who had no major protocol deviations, who received at least 90% of the prescribed amount of

VGT-309, and the surgeon first attempted to locate the tumor/nodule by adequate white light and palpation followed by adequate NIR imaging.

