1.1 Background and Rationale

Non-small cell lung cancer (NSCLC) is a particularly lethal cancer for which the best opportunity for cure comes from early detection and complete resection at surgery. Great advances in minimally invasive surgery (robotics; video-assisted thoracic surgery) have provided the opportunity to reduce the impact of major lung resection on the subject with lung cancer.

Minimally invasive surgery has come at the cost of increasing difficulty in localizing small cancers deep in the lung parenchyma due to the elimination of the ability to palpate the lung through a large thoracotomy incision. Currently this is overcome by one of three methods: a) remove a larger amount of tissue than required for biopsy of a suspicious lesion; b) wait until a suspicious lesion has grown sufficiently to allow easier detection at surgery; or c) perform a thoracotomy.

None of these options is optimal. The first, because a large amount of lung may be unnecessarily removed if the lesion is not cancer; the second, because the opportunity for early curative surgery may be missed if the cancer spreads in the months waiting for it to grow further; and the third negates the proven benefit of minimally invasive surgery.

The use of a tumor-targeted, activatable fluorescent imaging agent that can be taken up and bound by cancer tissues and visualized by tumor-specific fluorescence under NIR light during the surgical procedure could solve this problem if the drug readily identified the lesion for the surgeon. This could allow early and well-targeted surgical biopsy and subsequent appropriate cancer surgery for the correctly identified population.

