8.3 Intra-operative Evaluations

During the surgery, the Surgeon/Investigator will first utilize standard surgical techniques using white light and/or palpation followed by *in situ* NIR fluorescence imaging using an NIR imaging system capable of detecting ICG for localization of the primary tumor and any potential synchronous or occult lesions and lymph nodes.

The number and location of pulmonary nodules and synchronous lesions that are visualized by standard techniques and/or by VGT-309 NIR fluorescence imaging will be recorded. Lymph nodes visualized by VGT-309 NIR fluorescence imaging will be identified and recorded by nodal station and zone.

Following extraction of any tumor/nodules, synchronous lesions, and lymph nodes, *ex vivo* NIR fluorescence imaging will take place in the operative suite prior to closing the surgical field.

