10. STATISTICS

The study analyses will be conducted in a GCP environment (ICH E6). All analyses will be pre-specified in a Statistical Analysis (SAP) and finalized prior to database lock. If the methods in the SAP do not agree with this protocol, the methods described in the SAP will govern the analysis.

Additional post-hoc statistical tests may be performed and will be further described in the SAP.

Quantitative data will be presented as a standard set of summary statistics (n, mean, standard deviation, median, minimum and maximum values). Categorical data will be expressed as frequency (%).

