10.1 Sample Size Determination

10.2 Populations for Analysis

The study includes three prospectively defined study populations.

1. The Safety Population includes any subject who received any amount of VGT-309.
2. The Intent to Treat (ITT) Population will include all patients who received any amount of VGT-309 and had surgery with NIR imaging after the surgeon first attempts to locate the tumor/nodule by white light palpation.
3. The Evaluable Population (EP) will include the subset of ITT patients who were eligible, who had no major protocol deviations, who received at least 90% the prescribed amount of VGT-309, and the surgeon first attempted to locate the tumor/nodule by adequate white light and/or palpation followed by adequate NIR imaging.

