## **9. EFFICACY ANALYSES**

### **9.1. Definition of the Primary Efficacy Endpoint**

The proportion of subjects with at least one Clinically Significant Event (CSE) as defined by:

1. Intraoperative localization of one or more preoperatively identified lung lesions using VGT-309 with NIR imaging when standard surgical techniques using white light and/or palpation failed to identify the lesion(s), and lesion(s) are confirmed by histologic examination to be other than normal lung tissue.

2. Identification of one or more synchronous or occult lung lesions using VGT-309 with NIR imaging when standard surgical techniques using white light and/or palpation and preoperative imaging failed to identify the lesion(s), and lesion(s) are confirmed by histologic examination to be cancerous or precancerous.
3. Identification of fluorescence within  $\leq 10$  mm from the inside edge of the closest staple line as measured by the investigator *ex vivo* in the operating room using NIR imaging, with pathologic margin confirmed by histologic examination to be  $\leq 10$  mm. NOTE: Margins from excisions of known or suspected metastases at the time of the surgery, OR diagnostic wedge resections where a completion lobectomy or segmentectomy was subsequently performed, will not be considered for Margin CSE inclusion.
4. Identification of lymph nodes by VGT-309 with NIR imaging confirmed by histologic examination to be cancerous.

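### The SAP's Evaluable and ITT definitions require white light and palpation, whereas the protocol and the endpoint accept either, so a literal reading excludes permitted white-light-only cases

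*SAP*

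**What the plan says.** The two Evaluable definitions differ in one conjunction. SAP 7.3.4 requires that "the surgeon first attempted to locate the tumor/nodule by adequate white light and palpation followed by adequate NIR imaging"; protocol 10.2 requires that "the surgeon first attempted to locate the tumor/nodule by adequate white light and/or palpation followed by adequate NIR imaging".

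The SAP's ITT definition (7.3.3) also uses *and*: subjects who "had surgery with NIR imaging after the surgeon first attempts to locate the tumor/nodule by white light and palpation". The protocol's ITT text (10.2) has no conjunction: subjects who "had surgery with NIR imaging after the surgeon first attempts to locate the tumor/nodule by white light palpation".

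Elsewhere the rule is *and/or*. Protocol 8.3 says that the surgeon "will first utilize standard surgical techniques using white light and/or palpation followed by" NIR imaging. The first two CSE types in SAP 9.1 apply "when standard surgical techniques using white light and/or palpation failed to identify the lesion(s", and SAP 3.1 and protocol 2.2.1 define them in the same way. The primary hypothesis says *and/or* in protocol 10.3.2 but *and* in SAP 9.2.

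Protocol section 10 settles precedence: "If the methods in the SAP do not agree with this protocol, the methods described in the SAP will govern the analysis". Both documents put the primary analysis in the Evaluable Population (protocol 10.3.2, SAP 9.3), and SAP 9.3 repeats it in the ITT population.

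**The concern.** The SAP conflicts with the protocol and also with itself. A subject examined by white light alone, as protocol 8.3 allows, can meet the CSE definition in SAP 9.1 and still be shut out of the population in which CSEs are counted. The ITT repeat does not bring that subject back, because the SAP's ITT definition has the same condition and the Evaluable Population is a subset of it.

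The excluded subjects may not be a random subset. Protocol 1.1 attributes the difficulty of localizing small, deep lesions in minimally invasive surgery to the "elimination of the ability to palpate the lung through a large thoracotomy incision". Cases in which palpation is hard or not attempted are close to the problem the agent is meant to address. At stake are the size of the primary analysis set, its power, and the population to which the estimated CSE rate applies.

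**Working it through.** **Step 1. The wording side by side.**

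| Place | SAP | Protocol |
|---|---|---|
| Evaluable Population | and (7.3.4) | and/or (10.2) |
| ITT | and (7.3.3) | no conjunction (10.2) |
| Primary hypothesis | and (9.2) | and/or (10.3.2) |
| CSE types A and B (SAP 1 and 2) | and/or (3.1, 9.1) | and/or (2.2.1) |
| Operative procedure | not restated | and/or (8.3) |

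The clear conflicts with the protocol are in the Evaluable definition and the hypothesis. The protocol's ITT text can be read either way.

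**Step 2. Reproduce the plan's figures.** From the protocol synopsis: null rate 10%, true rate 20%, two-sided 5%, 80% power. The normal approximation gives

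n = [(1.960 × √(0.10 × 0.90) + 0.842 × √(0.20 × 0.80)) / 0.10]² = 85.5, rounded up to 86.

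This matches the plan. The Clopper-Pearson interval for 15/86 is 10.1% to 27.1%, which also matches. Under exact binomial probabilities, the rule of at least 15/86 has

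- P(X ≥ 15 | n = 86, p = 0.10) = 0.0230, within the one-sided 0.025;
- P(X ≥ 15 | n = 86, p = 0.20) = 76.3%.

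The stated 80% comes from the normal approximation. The planned test is exact, so 76.3% is the baseline for what follows.

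**Step 3. Room for losses.** About 100 enrolled less 86 needed leaves 14 non-evaluable subjects for all reasons. If 15 or more of 100 were not palpated, that alone would take the Evaluable Population below 86, unless subjects are replaced.

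**Step 4. Power by unpalpated share.** The documents do not give this share, so a range is assumed. The table takes 100 enrolled, no other losses and no replacement. For each n, the critical count is the smallest r with P(X ≥ r | p = 0.10) ≤ 0.025, and power is P(X ≥ r | p = 0.20).

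| Assumed share not palpated | n | Critical count | Exact power |
|---|---|---|---|
| 10% | 90 | 16 | 74.0% |
| 14% | 86 | 15 | 76.3% |
| 20% | 80 | 15 | 65.4% |
| 30% | 70 | 13 | 66.4% |
| 40% | 60 | 12 | 55.1% |
| 50% | 50 | 10 | 55.6% |
| 60% | 40 | 9 | 40.7% |

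Against 76.3%, the drop is 10.9 points at 20%, 9.9 at 30% and 20.7 at 50%. Power is not monotone in n because the test is discrete. At n = 79 the critical count is 14 and power is 73.6%, so n = 80 is a local low and should not be over-read.

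**Step 5. If the CSE rate differs by palpation status (illustration only).** Take an overall rate of 20% and 20% of subjects not palpated. The rate among those retained is (0.20 − 0.20 × r) / 0.80, where r is the rate among those excluded.

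- r = 20%: retained rate 20%, power at n = 80 is 65.4%.
- r = 25%: retained rate 18.8%, power 54.5%.
- r = 30%: retained rate 17.5%, power 42.9%.

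The documents give no value for r.

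**The case against.** The best defence is that *and* is deliberate. It appears in three places in the SAP. Requiring both techniques before NIR imaging would be a stricter comparator, and would guard against crediting the agent after a limited standard attempt. That is a coherent design. However, the SAP kept *and/or* in its own endpoint, the readable text gives no reason for the change, and there is no rule for subjects handled as protocol 8.3 permits. A deliberate restriction would need to be stated.

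Several objections to scope stand, and they rule out stronger readings that a reader might infer.

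- *Minimally invasive cases drop out as a class.* Not supported. Protocol 1.1 speaks of palpation through a large thoracotomy incision. It does not say that palpation is absent in minimally invasive surgery. The SAP requires only an attempt, and neither document says whether palpation with instruments counts or what makes an attempt adequate. Only subjects with no palpation attempt are clearly at risk.
- *The Evaluable Population will fall below 86.* Not established. Protocol 5.4 allows non-evaluable subjects to be replaced, and the synopsis and SAP section 4 allow expansion by amendment. These routes could restore the number, though not the excluded type of subject.
- *The CSE rate will be biased downward.* Possible but undocumented. No rate by palpation status is given, and the definitions of the margin and lymph-node events do not refer to palpation.
- *The SAP's ITT definition contradicts the protocol's.* The protocol's ITT text is garbled, so no contradiction can be shown there.

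**Conclusion.** The conflict is real and sits in the definition of the primary analysis set. Because the SAP governs, a literal reading removes every subject without a palpation attempt from both efficacy populations, against the protocol's own Evaluable definition, procedure and endpoint. Otherwise membership of the primary analysis set depends on how someone interprets the wording, in an open-label trial.

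The wording mismatch is certain; its consequences are conditional. With no other losses and no replacement, an unpalpated share up to 14% leaves at least 86 evaluable subjects. Shares of 20% to 50% would put exact power between about 55% and 66% at a 20% true rate, against 76.3% as planned. A lower CSE rate among retained subjects would reduce power further, but the documents neither show nor exclude this.

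**What to change.** Before database lock, change *and* to *and/or* between the two techniques in SAP 7.3.3, 7.3.4 and 9.2, and correct the protocol's ITT text in 10.2 to match. The analysis populations then agree with the endpoint and the operative procedure, and the planned 86 subjects and 15-event rule are unchanged.

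If the restriction is intended, state it, give the reason, and add an analysis that keeps white-light-only subjects.

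In either case, tabulate type A CSEs (type 1 in the SAP) by whether palpation was attempted. Protocol 8.3 asks for lesions seen by standard techniques to be recorded but does not ask which technique was used. If the technique is already captured, the cost is a wording change and one table. If not, a retrospective data query is needed as well, which is a small added cost.
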